### Background

Surgery can be an overwhelming and often a life-changing experience for patients. To mitigate this experience a patient-centered approach can be beneficial . Patient-centered care is defined as providing care that is "respectful of and responsive to individual patient preferences, needs and values, and which ensures that patient values guide all clinical decisions" . Patient-centeredness should be considered in discussions about the value of surgical treatment for the patient and the expectations regarding the process of postoperative rehabilitation, especially considering the patient's definition of a successful outcome . The meaning of rehabilitation may vary between stakeholders involved in surgery, including patients, surgeons, anesthetists, nurses, and hospital administrators . Studies addressing strategies to improve rehabilitation, such as minimally invasive surgery and enhanced recovery pathways, commonly focus on measures such as complication rates, gastrointestinal activity, physical function, and duration of hospital stay . These parameters are mostly relevant to clinicians and administrators, but they do not reflect the complexity of the rehabilitation process or include the patient's perspective and expectations.

In musculoskeletal practice, patients' expectations have been reported as a valuable predictor for treatment outcomes in patients with acute and chronic pain . Patients with higher expectations regarding the treatment report better outcomes than those with lower expectations . Previous studies have investigated the relationship between expectations and postoperative satisfactions in patients undergoing spinal surgery , and some evidence suggest patients' expectations also impact rehabilitation after surgery .

Patients undergoing spinal surgery usually suffer from moderate to severe pain during the perioperative and postoperative period , which is associated with developing persistent pain  and compromises patients' quality of life.

Lumbar disc herniation is one of the most common musculoskeletal diseases which, in some cases, can compromise patients' quality of life, and the most common operations performed on the spine . A previous study has shown that persistent pain after surgery for lumbar disc herniation is

negatively associated with psychological and physical well-being, and the overall quality of life is decreased .

We hypothesize that interviewing patients in a semi-structured manner would give unique perspectives on what is important to patients, as opposed to what is important to researchers. Further, we hypothesize that patients' preoperative expectations for spinal surgery can affect postoperative rehabilitation. Gaining in-depth understanding of the process of recovery from the patients' perspectives can, ultimately, guide patient-centered care and future research.

### **Aim**

The purpose of this study is twofold:

- 1) to investigate how expectations predict patients' pain, rehabilitation and quality of life after spinal surgery.
- 2) to explore the patients' expectations before, and their experiences after, spinal surgery regarding pain, rehabilitation and quality of life.

### **Methods**

#### Design

Prospective observational cohort study, where qualitative and quantitative data is collected. The study will illuminate the research question by using quantitative and qualitative approaches. No formal sample size calculation is performed since this is a prospective cohort study exploratory by nature.

#### Location of the study

The study will be conducted at the Department of Anesthesiology, Zealand University Hospital, Koege, from 01.09.2023 – 31.08.2024.

#### Participants

All patients at Zealand University Hospital, who meet the inclusion criteria, undergoing spinal

## PROTOKOL: Spinal surgery expectation

surgery during 1 year, will be invited to participate in the quantitative part of the study. We estimate that 300 patients will be eligible for the quantitative part. For the qualitative part, we will include 10 - 15 patients undergoing spinal surgery.

### *Inclusion criteria*

Patients must meet all the following criteria to be suitable for inclusion in the study.

Patients > 18 years, undergoing elective spinal surgery at Zealand University Hospital, Koege.

Patients able to read and understand Danish.

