### *Exclusion criteria*

Patients meeting one or more of the following criteria are ineligible for inclusion in the study.

Patients with cognitive deficits, such as dementia or who are mentally disabled and cannot cooperate with the study based on the investigator's judgement. Patients with alcohol and drug dependence based on the investigator's judgement.

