## **Data collection and analysis**

For the quantitative part the following background characteristics will be collected in a CRF: sex (male/female), age (years), Body Mass Index (BMI), preoperative opioid consumption (yes/no), civil status (response alternatives), job situation (response alternatives), and capable of working (yes/no). Questionnaires will be used for collection of data regarding pre-operative expectations (Treatment Expectation Questionnaire (TEX-Q) ), pain (Verbal rating scale (VRS)) functional level (Oswestry Disability Index (ODI) ) and quality of life (WHO Quality of Life – BREF (WHOQOL-BREF) ) and will be collected at baseline. Data regarding pain, functional level, and quality of life, will also be collected postoperatively. All questionnaires have been validated except the TEX-Q, which validation is under preparation.

The analyses will primarily focus on functional level and quality of life postoperatively as a function of preoperatively expectations. Other analyses will explore covariates as determinates of preoperative expectations and functional recovery. Data will be analyzed with multiple regression in SPSS. Results will be described with mean values and standard deviation of the mean value, or with median and inter-quartile range as appropriate. A 5% level of significance will be used. Relevant parametric or non-parametric methods will be used, depending on distribution of data.

For the qualitative part, data regarding pre-operative expectations, and their experiences 3 months post-operatively, will be collected using interviews. The interviews will be conducted using semi-structured questions, which will be designed prior to the interviews. Patients will be enrolled several days before surgery and will be interviewed during an in-person interview. The interviews will be recorded using an IPAD and in rooms suitable for asking emotional questions. The interviews will afterward be transcribed and analyzed by the investigators using inductive qualitative content analysis as described by Graneheim and Lundman. The data will then be divided into meaning units, condensed meaning units, codes and themes and discussed by the authors until consensus has been obtained.

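### Elective surgery at any spinal level is eligible, but function, one of two main outcomes, is measured only with a back-disability index, and spinal region is not among the listed data

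*Protocol*

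**What the plan says.** **Population.** Under Inclusion criteria, the surgical requirement is only that patients are "undergoing elective spinal surgery at Zealand University Hospital, Koege"; the other conditions are age and command of Danish. The Participants section invites "All patients at Zealand University Hospital, who meet the inclusion criteria, undergoing spinal" surgery over one year and expects about 300 to be eligible. The Exclusion criteria cover cognitive or mental impairment that prevents cooperation, and dependence ("Patients with alcohol and drug dependence based on the investigator's judgement"). Neither list mentions a spinal level or a type of operation.

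**Outcome.** Under Data collection and analysis, the function instrument is given as "functional level (Oswestry Disability Index (ODI", and no second function scale is named. The same section sets the priority: "The analyses will primarily focus on functional level and quality of life postoperatively as a function of preoperatively expectations".

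**Data items.** That section also states that "the following background characteristics will be collected in a CRF: sex (male/female), age (years), Body Mass Index (BMI), preoperative opioid consumption (yes/no"; the list ends with civil status, job situation and capability of working. Spinal region and type of operation do not appear.

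**Rationale.** The Background discusses surgery in general, musculoskeletal practice and spinal surgery. The one spinal condition it names is lumbar: "Lumbar disc herniation is one of the most common musculoskeletal diseases".

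**The concern.** The population is wider than the instrument. The ODI asks about limitation due to a back problem. A patient operated on for a neck disorder would state expectations about that operation, and would then have function scored on a scale built for another region. Aim 1 concerns how expectations predict the course after spinal surgery, and the ODI is the only function measure serving it.

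If neck-surgery patients are pooled with the rest, a weak expectation-function association could reflect the choice of scale and not the hypothesis. Under other conditions an association could be partly a difference between regions.

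Adding region as a covariate would not fully cure this. It removes a difference in mean score between regions but does not make a back-disability score measure neck or arm function. As the list of collected items stands, even that adjustment could not be made from those data. Population, instrument and collected variables are protocol decisions, so this is not simply something left to an analysis plan.

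**Working it through.** The Protocol gives no sample size calculation, power or effect size, so there is no stated figure to reproduce. The check is a comparison of sections, followed by an illustration of size.

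**Step 1: the sections side by side.**
- Who can enter: any elective spinal operation (Inclusion criteria), with no exclusion by region (Exclusion criteria).
- What is measured for function: the ODI alone (Data collection and analysis).
- What would allow separation by region: nothing in the listed items (same section).

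Followed as written, the plan puts any neck-surgery patients into a pooled ODI analysis.

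**Step 2: effect on the slope.**

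Inputs:
- N = 300, the Protocol's estimate of eligible patients.
- f, the share having neck surgery. It is not in the documents; the assumed range is 0.10 to 0.30.
- b, the slope of ODI on expectation score in back-surgery patients. It is not in the documents.
- Worst-case assumption: the slope is zero in neck-surgery patients.
- Equal within-group variance s² of the expectation score.

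Let d and D be the differences between groups (neck minus back) in mean expectation score and mean ODI. The pooled slope is

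[(1 − f)·b·s² + f(1 − f)·d·D] / [s² + f(1 − f)·d²]

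With equal means (d = D = 0) this reduces to (1 − f)·b:

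| Assumed f | Patients affected (300 × f) | Pooled slope |
|---|---|---|
| 0.10 | 30 | 0.90b |
| 0.20 | 60 | 0.80b |
| 0.30 | 90 | 0.70b |

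If the means differ, the term f(1 − f)·d·D enters. Suppose b is negative, so that higher expectations go with less disability, and neck-surgery patients score lower on the ODI (D < 0). If they also have higher expectations (d > 0), the extra term is negative and strengthens the apparent association. If they have lower expectations (d < 0), the term is positive and weakens it. The direction is therefore not fixed.

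**Step 3: effect on power, illustration only.** Further assumptions are a true correlation of 0.20 in back-surgery patients and 0 in neck-surgery patients, equal means and variances of both variables, and a two-sided 5% level (the Protocol gives 5% without sidedness). The pooled correlation is r = (1 − f) × 0.20, and power = Φ(atanh(r)·√(n − 3) − 1.96). The restricted analysis uses r = 0.20 and n = 300 × (1 − f).

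| Assumed f | Pooled r | Power, pooled (n = 300) | Restricted n | Power, restricted |
|---|---|---|---|---|
| 0 | 0.20 | 0.94 | 300 | 0.94 |
| 0.10 | 0.18 | 0.88 | 270 | 0.91 |
| 0.20 | 0.16 | 0.79 | 240 | 0.88 |
| 0.30 | 0.14 | 0.68 | 210 | 0.83 |

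As an example, at f = 0.10 restricted: atanh(0.20) = 0.2027, √267 = 16.34, product 3.31, minus 1.96 = 1.35, and Φ(1.35) = 0.91.

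Under these assumptions the restricted analysis has more power despite fewer patients, by about 3, 9 and 15 percentage points.

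**The case against.** **The number affected is unknown.** The Protocol never mentions neck surgery and gives no case mix. Neck patients are eligible only because nothing excludes them, and the share could be small or nil. This stands, and it is why the figures are a range under assumption.

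**The Protocol does not describe the ODI as a back index.** True. That is the general definition of the named instrument and does not depend on any study result. A reader might go further and infer that the ODI does not respond at all in neck patients, or that their scores sit at the floor. Nothing in the documents supports either reading. General items such as sleep or social life may respond partly, so zero signal is a worst case.

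**The bias need not be toward zero.** Correct. Attenuation follows only from the equal-means case.

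**The rationale is not purely lumbar.** Also correct. Lumbar disc herniation enters only at the end of the Background, and the Aim speaks of spinal surgery. The mismatch rests on the eligibility criteria and the instrument, not on the rationale.

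**The study is exploratory, and an analysis subset could be set in an analysis plan.** The first part limits the seriousness of the point. The second holds only if region is available, and the listed items do not provide it.

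**Conclusion.** The mismatch is real and should be corrected. Neck-surgery patients are eligible as written, function is assessed only with a back-disability index, and the listed items do not allow region to be separated.

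The loss of slope is 10% to 30% for an assumed neck share of 0.10 to 0.30, if the ODI carries no signal in those patients and group means and variances are equal. A smaller share or partial ODI response would make the loss smaller. With unequal means, the distortion could be in either direction.

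A reader might infer that the function part of Aim 1 cannot be answered. The documents do not support that. For back-surgery patients the ODI fits, and a moderate attenuation does not leave the question unanswered. The problem is confined to function: the verbal rating scale for pain and the WHOQOL-BREF are not tied to a spinal region, so the other main outcome is unaffected.

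**What to change.** 1. In Data collection and analysis, add spinal region to the items collected in the CRF. The documents do not say that it is available from another source, so it needs its own entry.
2. In the same section, restrict the main ODI analysis to lumbar or thoracolumbar surgery, state how purely thoracic operations are classified, and limit the function conclusion to back surgery.
3. Keep all eligible patients in the WHOQOL-BREF and pain analyses.
4. If neck surgery is not meant to be included, say so under Inclusion criteria; that alone would settle the point.

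The change costs one data item and a few sentences, and no patient's treatment is affected. The downside is a smaller ODI sample (270 to 210 of 300 over the assumed range) and no conclusion about function after neck surgery. If the sponsor wants that conclusion, the alternative is to add a function measure suited to neck patients and analyse by region, at the price of another questionnaire and a small subgroup.

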### *Exclusion criteria*

Patients meeting one or more of the following criteria are ineligible for inclusion in the study.

Patients with cognitive deficits, such as dementia or who are mentally disabled and cannot cooperate with the study based on the investigator's judgement. Patients with alcohol and drug dependence based on the investigator's judgement.

### *Procedure for patients who withdraw from the trial*

In accordance with the Declaration of Helsinki , patients have the right to withdraw from the study at any time for any reason. It will be recorded in the patient's Case Report Form if a reason is given.

## **Data collection and analysis**

For the quantitative part the following background characteristics will be collected in a CRF: sex (male/female), age (years), Body Mass Index (BMI), preoperative opioid consumption (yes/no), civil status (response alternatives), job situation (response alternatives), and capable of working (yes/no). Questionnaires will be used for collection of data regarding pre-operative expectations (Treatment Expectation Questionnaire (TEX-Q) ), pain (Verbal rating scale (VRS)) functional level (Oswestry Disability Index (ODI) ) and quality of life (WHO Quality of Life – BREF (WHOQOL-BREF) ) and will be collected at baseline. Data regarding pain, functional level, and quality of life, will also be collected postoperatively. All questionnaires have been validated except the TEX-Q, which validation is under preparation.

The analyses will primarily focus on functional level and quality of life postoperatively as a function of preoperatively expectations. Other analyses will explore covariates as determinates of preoperative expectations and functional recovery. Data will be analyzed with multiple regression in SPSS. Results will be described with mean values and standard deviation of the mean value, or with median and inter-quartile range as appropriate. A 5% level of significance will be used. Relevant parametric or non-parametric methods will be used, depending on distribution of data.

For the qualitative part, data regarding pre-operative expectations, and their experiences 3 months post-operatively, will be collected using interviews. The interviews will be conducted using semi-structured questions, which will be designed prior to the interviews. Patients will be enrolled several days before surgery and will be interviewed during an in-person interview. The interviews will be recorded using an IPAD and in rooms suitable for asking emotional questions. The interviews will afterward be transcribed and analyzed by the investigators using inductive qualitative content analysis as described by Graneheim and Lundman. The data will then be divided into meaning units, condensed meaning units, codes and themes and discussed by the authors until consensus has been obtained.

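### Every elective spinal operation is admitted, but no surgical variable is listed for collection, so as written the primary regression cannot adjust for the operation and the cohort cannot be described by it

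*Protocol*

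**What the plan says.** The Inclusion criteria in the Protocol take adults "undergoing elective spinal surgery at Zealand University Hospital, Koege" who read and understand Danish. The Exclusion criteria concern cognitive deficits and alcohol or drug dependence only. Neither list limits the procedure, spinal level, indication or surgical history. Under Participants the sponsor writes "We estimate that 300 patients will be eligible for the quantitative part".

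Under Data collection and analysis, "the following background characteristics will be collected in a CRF": sex, age and BMI, followed by "preoperative opioid consumption (yes/no), civil status (response alternatives), job situation (response alternatives), and capable of working (yes/no". The questionnaires add expectations (TEX-Q), pain (VRS), function (ODI) and quality of life (WHOQOL-BREF) at baseline, with the last three repeated after surgery. None of these is a surgical variable.

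The same section sets the main analysis: "The analyses will primarily focus on functional level and quality of life postoperatively as a function of preoperatively expectations", by multiple regression. It names no restriction or stratification by operation.

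The Background states the hypothesis that "preoperative expectations for spinal surgery can affect postoperative rehabilitation". Aim 1 is worded differently: "to investigate how expectations predict" pain, rehabilitation and quality of life.

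**The concern.** The operation could plausibly shape both what a patient expects beforehand and how the patient recovers. If so, a difference that belongs to the operation could be read as an effect of expectations, or could hide one. A regression can adjust only for what has been recorded, so this is more than a choice of covariates that an analysis plan could settle alone. Someone has to arrange for the data.

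A second problem does not depend on any causal claim. Part of the Background concerns a single indication ("persistent pain after surgery for lumbar disc herniation is" the subject of one cited result), while the cohort is open to all elective spinal surgery. Without the operation on record, the report could not say which kinds of surgery its findings describe. The protocol also plans to explore determinants of expectations and of functional recovery, and the operation is an obvious candidate for that analysis.

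**Working it through.** The protocol gives no effect size, case mix or power, so there is no figure of its own to reproduce. The check has two parts.

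**Reading.** Eligibility is open to any elective spinal operation. The listed background items, questionnaires and postoperative measures contain nothing about the operation. The identification list under Protection of patient data holds names and CPR numbers, so records could be traced, but no section plans to extract surgical data from them.

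**Illustration of possible size.** From the protocol: n = 300 (the estimate of eligible patients) and a 5% significance level, taken as two-sided because the sides are not stated. Everything else is assumed: two operation types with shares p and 1−p; within-type SDs of 1; differences between types of dx in expectations, dy in postoperative outcome and db in baseline outcome; within-type correlation of baseline and postoperative outcome 0.5; and no true effect of expectations.

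With v = p(1−p), the unadjusted correlation of expectations and outcome is

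r_xy = dx·dy·v / √[(1+dx²v)(1+dy²v)].

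For dx = dy = 0.5 and p = 0.5, v = 0.25 and r_xy = 0.0625/1.0625 = 0.0588. The chance of a significant result is Φ(m−1.96) + Φ(−m−1.96) with m = atanh(r)·√(n−3). Here m = 0.0589 × √297 = 1.015, which gives 17.4%. Other splits and sizes:

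| Split | r_xy | n = 300 | n = 200 |
|---|---|---|---|
| 50/50 | 0.0588 | 17.4% | 13.1% |
| 20/80 | 0.0385 | 10.2% | 8.4% |
| 10/90 | 0.0220 | 6.7% | 6.1% |

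The baseline outcome is collected, so adjustment for it is possible. Then

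r_xb = dx·db·v / √[(1+dx²v)(1+db²v)],

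r_yb = (0.5 + dy·db·v) / √[(1+dy²v)(1+db²v)],

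partial r = (r_xy − r_xb·r_yb) / √[(1−r_xb²)(1−r_yb²)].

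For n = 300, a 50/50 split and dx = dy = 0.5 (n−4 replaces n−3):

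| Baseline difference db | r_xb | r_yb | partial r | False-positive rate |
|---|---|---|---|---|
| 0 (none present at baseline) | 0 | 0.4851 | 0.0673 | 21% |
| 0.5 (all present at baseline) | 0.0588 | 0.5294 | 0.0327 | 8.7% |
| 1.0 (twice the postoperative gap) | 0.1085 | 0.5423 | 0.0000 | 5.0% |
| −0.5 (equal and opposite) | −0.0588 | 0.4118 | 0.0913 | 35% |

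With differences of 0.2 SD instead (50/50, n = 300), r_xy = 0.01/1.01 = 0.0099 and the rate is 5.3% unadjusted. After baseline adjustment it is 5.4% with no baseline gap, and lower with a gap in the same direction.

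Masking is possible too. With a true within-type correlation of 0.15 and 0.5 SD differences of opposite sign, no covariates and a 50/50 split, the correlation becomes (0.15 − 0.0625)/1.0625 = 0.0824, and power at n = 300 falls from 74.0% to 29.6%.

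The other collected covariates (such as opioid use and capability of working) are not modelled.

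**The case against.** Four points weigh on the other side.

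First, the list under Data collection and analysis is of background characteristics and need not be the whole CRF. The section on withdrawal puts a further item, the reason for withdrawing, in the CRF. This stands: not listed is weaker than not collected. A reader might infer that the protocol rules these data out, and it does not. It simply does not plan them.

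Second, the operation is in the hospital record at a single site and patients are identifiable, so the data could be retrieved later. This also stands. A reader might infer that the gap is beyond repair, but it can be mended if the extraction is planned.

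Third, if aim 1 is read as pure prediction in a study the protocol calls exploratory, an unadjusted association is not biased. That is correct. The confounding argument rests on the hypothesis in the Background that expectations can affect rehabilitation. The inability to describe the cohort by operation remains under either reading.

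Fourth, all inputs to the illustration are assumed, and even the 0.5 SD case with an even split gives a spurious correlation of only 0.059, or 0.35% of variance (0.0588² = 0.0035). Rejection rates make a small bias look larger. This is fair, and the figures show only that bias is possible.

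**Conclusion.** The point holds on the text. Eligibility is open to every elective spinal operation, no surgical variable is among the listed data, and no retrieval is planned. Followed as written, the primary regression cannot adjust for the operation and the cohort cannot be described by it. The first consequence matters for the hypothesised effect; the second matters under any reading of the aim.

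The size and direction of any bias are unknown, because the protocol gives neither the case mix nor any link between operation and expectations. Under the assumed 0.5 SD differences and an even split, the false-positive rate is 17% unadjusted; at 0.2 SD the problem is negligible. A reader might infer that the main result will be biased, and the documents do not support that.

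Nor should one infer that adjusting for the baseline outcome settles the matter. It may absorb part of the difference, but in the illustration the rate runs from 8.7% when the whole postoperative difference is already present at baseline to 21% when none is. It reaches the nominal 5% only when the baseline gap is twice the postoperative one, and rises to 35% when the gap is reversed. The protocol should be changed, with medium confidence in how much this would alter the results.

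**What to change.** Under Data collection and analysis, add four CRF fields copied from hospital records: procedure type (for example discectomy, decompression, fusion, other), spinal level (cervical, thoracic, lumbar), indication, and previous spine surgery (yes/no). Describe the cohort by all four.

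Include procedure type, level and previous surgery in the primary regressions together with the baseline value of the outcome. Merge sparse categories once the case mix is known and before outcomes are analysed. Whether indication also enters can be decided by how far it overlaps with procedure type.

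The cost is record extraction for up to about 300 patients, with no new patient contact. The written consent and the reports to the Research Ethics Committee and the Danish Data Protection Agency must be checked for coverage of these fields and updated if they fall short.

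The models use at most 7 degrees of freedom (procedure 3, level 2, previous surgery 1, baseline 1). For a correlation of 0.15, replacing n−3 by n−10 in the Fisher z calculation lowers power from 74.0% to 73.0% at n = 300 and from 56.4% to 54.9% at n = 200. Overlap of the covariates with expectations could cost more.

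### Does the wording for the spread of results commit the study to standard errors in place of standard deviations, and leave the regression slope without an interval?

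*Protocol*

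**What the plan says.** Three statements under Data collection and analysis in the protocol bear on this point.

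- On summaries: "Results will be described with mean values and standard deviation of the mean value, or with median and inter-quartile range as appropriate".
- On the model: "Data will be analyzed with multiple regression in SPSS".
- On testing: "A 5% level of significance will be used".

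The same section gives the main question: "The analyses will primarily focus on functional level and quality of life postoperatively as a function of preoperatively expectations". On numbers, the Participants section says "We estimate that 300 patients will be eligible for the quantitative part", and the Design section says "No formal sample size calculation is performed since this is a prospective cohort study exploratory by nature".

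The protocol gives no SD for any questionnaire score. It does not say how regression coefficients will be presented, and it neither mentions nor rules out confidence intervals.

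**The concern.** In standard usage, the standard deviation of a mean is the standard error. It shrinks as the sample grows and says nothing about how much patients differ. The protocol admits adults having any elective spinal surgery at one hospital, so differences between patients are something a reader needs to see. If the text were followed to the letter, tables could show standard errors for roughly symmetric variables and inter-quartile ranges for skewed ones. These two measures are not counterparts. A reader who took the first for a spread would think the cohort far more uniform than it is. Later investigators who used the figure as an SD to plan a study would plan one that is much too small.

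A second worry comes from the inferential side. The only criterion named is a 5% significance level, and there is no sample size calculation. If the association between expectation and outcome were reported by p-value alone, a non-significant result would not show whether a relevant association had been ruled out.

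**Working it through.** There is no figure in the plan to reproduce, because the protocol states no SD, power or target precision. The check is therefore the size of the discrepancy on the literal reading, followed by a reading of the sentence itself.

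**Inputs**
- n: 300 at most. The Participants section gives this as an estimate of eligible patients, not of patients enrolled or analysed. I take 200 and 150 as assumed lower values.
- SD of a score: not given. I assume 10, 15 and 20 points, for illustration only.

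**Ratio of SD to standard error**

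SD / (SD/√n) = √n, whatever the scale.

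| n analysed | √n |
|---|---|
| 300 | 17.3 |
| 200 | 14.1 |
| 150 | 12.2 |

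The ratio rounds to 17 only for n between 16.5² = 272.25 and 17.5² = 306.25, that is, about 273 to 306. A factor of 17 therefore needs nearly every eligible patient to be enrolled and to have data.

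**What a table would show on the literal reading (SD/√n)**

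| Assumed SD | n = 300 | n = 150 |
|---|---|---|
| 10 | 0.58 | 0.82 |
| 15 | 0.87 | 1.22 |
| 20 | 1.15 | 1.63 |

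Figures this small on a questionnaire score would stand out, and a standard error labelled as such converts back to the SD by multiplying by √n.

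**Which quantity the sentence means**

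The sentence sets two options side by side, with the choice made as appropriate; the section goes on to tie its choice of methods to the distribution of the data. The second option is a location with a between-patient spread (median, inter-quartile range). The natural first option is likewise a location with a between-patient spread (mean, SD). The standard error has no place in that pairing. The sentence itself therefore points to the ordinary SD.

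**The interval for the slope**

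The sentence on means and medians covers descriptive summaries. The sentence on multiple regression names the method and the software, and the one on significance names the level. None of them limits reporting to p-values.

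For scale only: the 95% half-width for a simple correlation near zero, on the Fisher z scale, is 1.96/√(n − 3).
- n = 300: 1.96/√297 = 0.114
- n = 150: 1.96/√147 = 0.162

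These values show why an interval is informative. They are not the widths for a coefficient from the planned multiple regression, and they do not show that the interval will be missing.

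**The case for a change.** The strongest case for a change is that this is not an omission. The protocol names a statistic, and the one it names is the wrong one for the purpose. Two readings are open, they differ by a factor of roughly 12 to 17, and an analyst who followed the text could properly report standard errors. Removing one phrase would settle it at no cost. In a study with no sample size calculation that hopes to guide later research, a correct spread for the expectation score and the outcome scores matters.

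Part of this stands. The wording is imprecise, and its literal meaning is the standard error. The arithmetic is right under its conditions. What does not stand is the step from the wording to a likely error in the results. Harm would need an analyst to take the odd literal reading over the one the sentence itself suggests, and then to print the standard error without a clear label.

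The argument about the slope is weaker still, because it treats silence as a decision. Giving coefficients with 95% confidence intervals is good practice, but the absence of that detail from a protocol is not a defect when a statistical analysis plan may supply it. The absence of a sample size calculation is stated openly and does not make the descriptive wording any worse.

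**Conclusion.** The concern does not call for a change to the plan. The phrase is a clerical slip for the ordinary standard deviation, and the pairing in the same sentence makes the intended meaning clear enough for any analyst to fill it in sensibly. Only on a literal reading would the reported spread be too small: by a factor of 12.2 at 150 patients, 14.1 at 200, and 17.3 at the ceiling of 300. The two smaller numbers are assumptions, and 300 is the protocol's estimate of eligible patients. Correcting the label would alter no regression model, estimate, test or conclusion about expectation and outcome. The claim that the slope will be reported without an interval has no support in the text. This conclusion rests on the analysts reading the sentence as it is built. Tables that label their measure of spread would confirm it.
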